Official Title

The Learning Outcome of Resuscitation Teamwork Training on
Developing Teamwork Performance in Postgraduate Year
Doctors and Nurses - Comparison of Board Game-based
Learning, Simulation-based Learning and lecture-based learning

- **ClinicalTrials.gov ID:** NCT05302414
- **Protocol ID:** N201912063 (Taipei Medical University-Joint Institutional Review Board)
- **Document date:**
 - **Application Form:** Version 3.0 / 20220623
 - **Other Appendix:** Version 2.0 / 20220623
 - **Informed Consent Forms:** Version 2.0 / 20220211
 - **Protocol Version/ Date:** Version 2.0 / 20220211
 - **Case Report Forms:** Version 1.0 / 20220110

Objectives:

The aim of this study was to compare the effectiveness of board game-based learning, simulation-based learning, and interactive lecture-based learning in enhancing resuscitation medical knowledge, teamwork knowledge, medical task performance, and teamwork performance among postgraduate-year residents and nurses undergoing resuscitation teamwork training.

Methods:

Utilizing a single-blind, prospective, randomized controlled trial approach, this study enlisted 96 postgraduate-year nurses and physicians through convenience sampling. The participants were divided into three groups: the Board Game-Based Learning Group (Experimental Group I), the Simulation-Based Learning Group (Experimental Group II), and the Interactive Lecture-Based Learning Group (Control Group), with each group comprising 32 individuals. Evaluations of effectiveness were conducted at three points: pretest, posttest, and at a three-month follow-up. The instruments for measurement included assessments of team performance observation tool, knowledge of teamwork assessment, interprofessional collaboration scale, resuscitation knowledge scale, medical task performance, learning cognitive load, and course survey. Two evaluators, unaware of which teaching method the team received, independently used standardized assessment forms to evaluate the medical team's resuscitation actions and teamwork behavior in scenario-based simulations through video observation, ensuring objectivity and reliability.

Statistical:

In this study, the presentation of categorical variables was conducted using frequencies and percentages, while continuous variables were summarized through means and standard deviations. The chi-squared test was applied to examine the demographic characteristics at the outset. Given the data's deviation from a normal distribution, a non-parametric approach was adopted for analysis, with the median and interquartile range (IQR) providing insights into the data's central tendency and dispersion. This method, unaffected by outliers, offers a more accurate depiction of data that does not follow a normal distribution. To identify differences across the three groups, the study utilized the Kruskal-Wallis H-test. The Friedman test was used to evaluate changes within groups, whereas the Wilcoxon test facilitated pairwise comparisons at various assessment points. GEE analysis was employed to compare the effectiveness of the intervention across different time points among the three groups. Text mining techniques were used to analyze feedback from course collections. IBM SPSS version 20 was the tool for all data analyses. The criteria for statistical significance were established using a two-tailed test, setting the P-value threshold at < 0.05 .

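### Nurses and physicians are enrolled together, but no stratification by profession is reported and neither stated between-arm analysis includes profession, which costs precision in single-time-point comparisons

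*Combined protocol and SAP*

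**What the plan says.** The Objectives concern "teamwork performance among postgraduate-year residents and nurses undergoing resuscitation teamwork training", so two professions define the population. The Methods section describes the design as "Utilizing a single-blind, prospective, randomized controlled trial approach". It reports that "this study enlisted 96 postgraduate-year nurses and physicians through convenience sampling. The participants were divided into three groups", "with each group comprising 32 individuals". No allocation procedure follows: no sequence, blocks, strata or rule for making up teams. The number of nurses and of physicians is not given.

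In the Statistical section, profession could enter at only one place, the baseline check: "The chi-squared test was applied to examine the demographic characteristics at the outset". Profession is not named there, and the test describes imbalance without adjusting for it. Two analyses compare the arms. One is a rank test: "To identify differences across the three groups, the study utilized the Kruskal-Wallis H-test". The other is a GEE across groups and time points, for which no covariates of any kind are listed.

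**The concern.** Profession is known for every participant before allocation. It could plausibly predict several outcomes: resuscitation knowledge, medical task performance and interprofessional collaboration. Convenience recruitment leaves the nurse:physician ratio to whoever is available.

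If profession predicts the score and the analysis ignores it, two things follow.

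- The between-profession variance stays in the error term and lowers power, even when the arms happen to balance.
- If allocation was not stratified, the arms can differ by chance in their share of physicians. Part of an observed difference between teaching methods in this one trial could then reflect professional mix.

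The baseline chi-squared test is weak protection against the second, because it has little power to detect imbalances of the size that matter here.

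**Working it through.** **Inputs from the documents.** 96 participants, three arms of 32 (3 × 32 = 96, consistent), two-sided 0.05. The documents give no power calculation, so there is no power figure to reproduce.

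**Assumptions, not in the documents.** 48 nurses and 48 physicians; individual, independent, normally distributed scores; within-profession SD of 1; nurse-physician gap D of 0.5, 0.8 or 1.0 SD, with 0 as reference; allocation that ignores profession.

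**Step 1: variance left in the error.** With physician share p, total SD = √(1 + p(1−p)D²). At p = 0.5:

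- D = 0.5: √1.0625 = 1.031
- D = 0.8: √1.16 = 1.077
- D = 1.0: √1.25 = 1.118

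The between-profession part is 6%, 14% and 20% of total variance.

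**Step 2: normal-theory check for one pair of arms.** Detectable difference at 80% power = SD × √(2/32) × (1.96 + 0.84). With profession adjusted for, this is 1 × 0.25 × 2.80 = 0.70. Unadjusted, it is 0.72, 0.75 and 0.78. Power for a true 0.70 SD difference falls from 80% to 78%, 74% and 71%. At a 25:75 mix it falls to 78%, 75% and 73%.

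**Step 3: simulation of the planned test.** Three arms, one of them better by 0.7 SD, a single time point, 5,000 trials per setting. Ranges show the spread over repeated runs.

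| Gap D | Kruskal-Wallis | Rank ANCOVA with profession |
|---|---|---|
| 0 | about 80% | about 80% |
| 0.5 | 76-77% | 78-80% |
| 0.8 | 73-74% | 79-80% |
| 1.0 | 68-69% | 78-80% |

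Type I error was about 5% for both methods at every gap.

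**Step 4: change from pretest.** If the gap is the same at both times, D cancels from post minus pre. The SD of the change is √(2(1−ρ)), which is 1 at an assumed within-profession correlation ρ of 0.5. Kruskal-Wallis on change then had 79-80% power at every gap, 0 included.

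**Step 5: chance imbalance.** The SD of the difference in physician share between two arms is √(2/32 × 0.25 × 96/95) = 0.126. In 200,000 simulated allocations:

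- For a given pair of arms, the median absolute difference is 9.4 points and the 95th percentile is 25 points. About 10% of allocations exceed 20 points.
- The largest of the three pairwise differences exceeds 20 points in about 23% of allocations. In about 78% of those the chi-squared P-value is 0.05 or more. Differences up to 28 points (9/32) can pass.
- The shift in a contrast is imbalance × D. At 25 points it is 0.13, 0.20 or 0.25 SD for D of 0.5, 0.8 or 1.0. At the median it is 0.05 to 0.09 SD for D of 0.5 to 1.0. The standard error of a 32-versus-32 contrast is √(2/32) = 0.25 SD.

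**The case against.** The strongest reply is that the documents are silent, and silence does not show that profession was ignored. Allocation is not described at all, so stratification cannot be ruled out. Teams may also have been formed with a fixed nurse:physician make-up. In that case the arms would balance by construction and every figure in step 5 would be zero. This stands: the supportable statement is that no such control is reported.

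A reader might also infer that differences in professional mix bias the comparison of teaching methods. The documents do not support that. They call the trial randomised; under randomisation chance imbalance averages out, and the simulated type I error stays near 5%. The 25-point shifts are tail values, and the typical shift is well below the standard error of the contrast.

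The power loss is also narrower than it may seem. A pretest exists, and the GEE compares arms over time points. If it tests group-by-time change, a stable profession gap largely cancels. Protection is lacking for Kruskal-Wallis on scores at a single time point, and in either analysis if the professions differ in how much they learn.

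Finally, the video ratings assess teams. The figures assume individual scores and say nothing about the size of any effect on team ratings. The documents are in the past tense, so a change to allocation is probably too late.

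What survives is the analysis point: a value known for every participant is left out of both stated between-arm methods.

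**Conclusion.** The point holds as a matter of efficiency. As stated, neither between-arm analysis uses profession, and no stratification or fixed team composition is reported. For individual-level outcomes compared at one time point, the cost is about 2 to 3 points of power at a gap of 0.5 SD and about 10 to 11 at 1.0 SD. It is nil at no gap, and essentially nil for change from pretest with a stable gap. These sizes rest on an assumed 48/48 split and an assumed gap; the documents give neither, so the effect runs from negligible to material.

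For the individual trial, a non-significant baseline chi-squared test is not a sound reason to leave profession out. The documents do not support a claim of systematic bias, of an inflated overall type I error, or of any particular effect on team-rated outcomes.

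**What to change.** **Individual-level outcomes.** Include profession (nurse or physician) as a fixed covariate in the GEE. Replace the unstratified Kruskal-Wallis at each time point with a profession-stratified rank test (van Elteren-type) or a rank ANCOVA with profession. Do this whatever the baseline chi-squared P-value. If results have already been seen, report it as a post hoc adjusted analysis beside the unadjusted one in the plan.

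**Team-rated outcomes.** State the nurse:physician composition of the teams in each arm, and make no claim about the size of any profession effect.

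**Allocation.** State whether it was stratified by profession. Only if it is not complete, randomise within each profession and give teams the same composition in all three arms.

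**Cost.** One covariate that should already be held for everyone, one degree of freedom, and a sentence each in the Methods and Statistical sections. No extra participants or measurements are needed. The power gain was simulated for rank ANCOVA only, not for the GEE or the stratified rank test.

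### Scores presumably taken per person are probably correlated within training team, but the planned group comparison treats the 32 people per arm as independent

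*Combined protocol and SAP*

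**What the plan says.** The Methods section of the combined protocol and SAP states that "this study enlisted 96 postgraduate-year nurses and physicians through convenience sampling". On allocation it says only that "The participants were divided into three groups", "with each group comprising 32 individuals".

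The same section describes the video raters: "Two evaluators, unaware of which teaching method the team received, independently used standardized assessment forms". Their task was "to evaluate the medical team's resuscitation actions and teamwork behavior in scenario-based simulations through video observation". The other instruments are listed without a unit of scoring, among them "knowledge of teamwork assessment, interprofessional collaboration scale, resuscitation knowledge scale" and a cognitive load measure.

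The Statistical section gives the between-group test: "To identify differences across the three groups, the study utilized the Kruskal-Wallis H-test". It adds the Friedman and Wilcoxon tests for change within groups, and a GEE for the comparison of arms over the three assessments. It does not name the GEE cluster variable or working correlation.

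Neither section gives the unit of randomisation, the number or size of teams or sessions, the assignment of instructors, or an intraclass correlation (ICC).

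**The concern.** The course trains teamwork, and the rater sentence names the team as the recipient of the teaching. People taught together share what happened in their group: its pace, its discussion and its co-learners. Their scores afterwards are likely to resemble each other more than those of people taught in different groups of the same arm.

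Kruskal-Wallis takes its reference distribution from independent observations. With positive correlation inside teams, the arm rank sums vary more by chance than the test allows, so it rejects too often. A GEE does not necessarily repair this. If its cluster is the participant, it allows for repeated visits but not for shared teaching.

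The point is easy to miss because 32 per arm looks like the right count for a score that belongs to a person. Two of the four aims in the Objectives section are knowledge outcomes of this kind. The video-rated outcomes raise a separate question, namely how a score given to a whole team is counted. Settling that would leave the present point untouched.

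**Working it through.** **The plan's own figure.** 3 × 32 = 96, which agrees with the stated total. No effect size, standard deviation or power is given, so the sample size cannot be reproduced further. For reference, with independent people and a two-sided 5% two-arm comparison, 32 per arm detects a standardised difference of (1.960 + 0.842) × √(2/32) = 0.70 with 80% power.

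**Inputs.** From the documents: three arms, 32 per arm, Kruskal-Wallis, two-sided 0.05. Assumed, because the documents are silent: team size m of 4 or 8 (8 or 4 teams per arm) and ICC of 0.01, 0.05, 0.10 or 0.20.

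**Formulas.**
- Design effect: DE = 1 + (m − 1) × ICC.
- Effective number per arm: 32 / DE.
- Factor by which the standard error is understated: √DE.
- Hand check on the rejection rate: with three arms the statistic is referred to chi-squared on 2 degrees of freedom, whose upper tail at x is exp(−x/2). Inflating the statistic by DE turns 0.05 into about 0.05^(1/DE).

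The last column is a direct simulation: 20,000 null trials per setting, normal scores with a shared team effect, Kruskal-Wallis at 0.05.

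| m | ICC | DE | Effective n per arm | √DE | 0.05^(1/DE) | Simulated rejection |
|---|---|---|---|---|---|---|
| 4 | 0.01 | 1.03 | 31.1 | 1.015 | 0.055 | 0.053 |
| 4 | 0.05 | 1.15 | 27.8 | 1.072 | 0.074 | 0.070 |
| 4 | 0.10 | 1.30 | 24.6 | 1.140 | 0.100 | 0.097 |
| 4 | 0.20 | 1.60 | 20.0 | 1.265 | 0.154 | 0.146 |
| 8 | 0.01 | 1.07 | 29.9 | 1.034 | 0.061 | 0.056 |
| 8 | 0.05 | 1.35 | 23.7 | 1.162 | 0.109 | 0.106 |
| 8 | 0.10 | 1.70 | 18.8 | 1.304 | 0.172 | 0.164 |
| 8 | 0.20 | 2.40 | 13.3 | 1.549 | 0.287 | 0.284 |

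Worked line, m = 8 and ICC = 0.20: DE = 1 + 7 × 0.20 = 2.40; 32 / 2.40 = 13.3; √2.40 = 1.549; 0.05^(1/2.40) = 0.287.

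**Checks.** With ICC = 0 the simulated rates are 0.046 (m = 4) and 0.048 (m = 8), so the test itself is sound when people are independent. The simulation error at the top rate is √(0.284 × 0.716 / 20,000) = 0.003. A separate run of 8,000 trials per setting gave 0.074, 0.098 and 0.144 for m = 4, and 0.099, 0.170 and 0.287 for m = 8, at ICC 0.05, 0.10 and 0.20.

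**Larger sessions.** If the shared unit were a session of 16 (two per arm), the simulated rates would be 0.071, 0.175, 0.294 and 0.477 over the same four ICC values.

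The simulation concerns one Kruskal-Wallis test at one post-training assessment. It says nothing about the GEE, whose specification is not given.

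**The case against.** The strongest reply is that the key sentence is about blinding. It tells the reader what unit the raters scored, and only in passing how teaching was delivered. The allocation sentence speaks of participants and individuals. The wording would also fit people taught arm by arm and put into teams for the filmed scenario. This stands in part: the text indicates team delivery but does not describe it, so the conclusion must stay conditional.

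Several stronger readings are tempting, and the documents do not support them.

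- *Team-mates shared a session and an instructor.* Neither is mentioned. An instructor common to all arms would add no error between arms. One instructor per arm would be confounding, which is a different problem.
- *The knowledge, collaboration and cognitive load scales were scored per person.* This is the natural reading, but it is not stated.
- *The GEE ignores teams.* Its cluster variable is unstated. That is a gap in reporting and does not demonstrate a wrong analysis. Even with the team as cluster, the separate Kruskal-Wallis test would be uncorrected, and the usual sandwich standard error is too small with only 4 to 8 teams per arm.
- *The error rate is certainly badly inflated.* At ICC 0.01 it is 5.3% to 5.6%, close to nominal.

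It is also fair to say that shared teaching cannot affect the pretest, so the point is limited to the posttest and the three-month follow-up.

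**Conclusion.** The point holds in conditional form. If participants were taught in teams, as the Methods section indicates, the stated between-group test is too liberal for any positive correlation within team, and the plan names nothing that would correct it. The direction does not depend on the assumed values, but the size does. For teams of 4 to 8 and ICC 0.01 to 0.20 the true rejection rate is about 5% to 29% against a nominal 5%, and the standard error is understated by a factor of about 1.02 to 1.55. The documents do not allow a narrower range.

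This rests on team delivery and on individual scoring of the scales, both inferred. A reader might go further and conclude that differences between instructors have been mistaken for differences between teaching methods. Nothing in the documents shows who taught whom, so that cannot be said.

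**What to change.** State the unit of randomisation, the number and size of training teams and sessions, which instructor taught each, and the GEE cluster variable and working correlation.

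For outcomes scored per person after training, replace the participant-level Kruskal-Wallis comparison with one of the following:
- a GEE or mixed model with the training team (or the session, if larger) as the cluster, visits nested within it, and a small-sample correction;
- a permutation test that shuffles whole training teams between arms. With 4 teams per arm there are 12! / (4!)³ = 34,650 arrangements, which is ample. With only two sessions per arm there are 6! / (2!)³ = 90. Each value of a three-arm statistic then occurs at least 3! = 6 times, so the smallest p-value is 6/90 = 0.067 and the test cannot reach 0.05.

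If an arm had a single session or a single instructor, no model can separate that from the teaching method. It should then be reported as a limit on the conclusion. Rotating instructors across formats would be a design change. The text is written in the past tense, so it is not proposed here if training is complete.

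The cost is a team or session identifier and an instructor code per participant, a few lines of SAP text, and wider intervals. At a design effect of 2.4 the standard error grows by about 55%. Power for a standardised difference of 0.70 in a two-arm comparison then falls from 0.80 to 0.44; at a design effect of 1.03 it is 0.79. If team rosters were kept, the analysis can be redone on existing data.

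### Team-rated outcomes: neither the unit of analysis nor the number of teams is stated, and the listed GEE needs a small-sample correction even if the team is the unit

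*Combined protocol and SAP*

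**What the plan says.** In the combined protocol and SAP, Objectives lists four outcomes. Two of them are "medical task performance, and teamwork performance among postgraduate-year residents and nurses". Methods lists seven instruments, beginning "The instruments for measurement included assessments of team performance observation tool"; medical task performance is another. It then says that two evaluators, "unaware of which teaching method the team received, independently used standardized assessment forms to evaluate the medical team's resuscitation actions and teamwork behavior", worked from video of simulated scenarios.

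Size is stated in people only: "this study enlisted 96 postgraduate-year nurses and physicians through convenience sampling", split into three groups "with each group comprising 32 individuals". Team size, number of teams, whether people or teams were allocated, and whether teams stayed together over the pretest, posttest and three-month assessments are not given.

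The Statistical section covers all outcomes alike:

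- Between groups: "To identify differences across the three groups, the study utilized the Kruskal-Wallis H-test".
- Within groups: "The Friedman test was used to evaluate changes within groups, whereas the Wilcoxon test facilitated pairwise comparisons at various assessment points".
- Over time: "GEE analysis was employed to compare the effectiveness of the intervention across different time points among the three groups".

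No test is tied to an outcome. No unit is named for the rank tests, and no subject, cluster or working correlation for the GEE. No rule is given for combining the two evaluators' scores.

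**The concern.** A rating of a team's behaviour most naturally gives one score per team per time point. This is an inference, but it follows from what the evaluators are said to have assessed. The data file, however, may well hold 32 people per group. If each member's row carries the team's score, the same observation is counted several times, and the rank tests treat the copies as independent. A GEE with the participant as subject allows for correlation over time within a person but not for teammates sharing a score.

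If each team has one row, the rank tests are sound, but they rest on fewer units than a reader of the Methods section would suppose. The GEE then has few clusters, where the usual robust standard error is too small.

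Teamwork performance is in the title. A reader who cannot tell which analysis was done cannot judge a claimed difference between the three teaching methods on it.

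**Working it through.** **Inputs from the documents.** Three groups of 32 individuals, 3 × 32 = 96, which agrees with the stated total. Three assessments. Two-sided 0.05. There is no power calculation to reproduce.

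**Assumptions.** Team size m is not stated. I take m = 2, 4 and 8, which gives 32/m = 16, 8 and 4 teams per group. The GEE is also unspecified. I assume an identity link, independence working correlation, sandwich standard errors and a true correlation of 0.5 over time.

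**Case (a): team score copied to every member.** Copying each row m times multiplies the Kruskal-Wallis statistic by about m. With three groups the reference is chi-square on 2 df, with critical value 5.991, so the chance of rejecting under the null is about exp(−5.991/(2m)):

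- m = 2: exp(−1.498) = 22%
- m = 4: exp(−0.749) = 47%
- m = 8: exp(−0.374) = 69%

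For one GEE coefficient the analogous approximation is 2(1 − Φ(1.96/√m)) = 17%, 33% and 49%. Simulation under the null (full enumeration also available for Friedman) gives these rejection rates at nominal 5%:

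| Copied scores | m = 2 | m = 4 | m = 8 |
|---|---|---|---|
| Kruskal-Wallis | 22% | 50% | 75% |
| Friedman, one group | 23% | 53% | 65% |
| Signed-rank, one group | 17% | 36% | 50% |
| GEE, participant as subject, one group-by-time coefficient | 19% | 37% | 57% |

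Repeat runs agreed to within about one percentage point.

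**Case (b): one row per team.**

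- Kruskal-Wallis rejects about 4-5% at all three sizes, and Friedman by chi-square 5-7%.
- GEE with team as subject and no correction rejects about 6%, 9% and 13% for one coefficient, and 11%, 19% and 42% for the 4-df group-by-time interaction.
- With the Mancl-DeRouen correction and a t or F reference, both return to about 4-5%.

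**Limits of the rank tests with few teams.**

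- The smallest exact two-sided signed-rank p is 2/2ⁿ: 0.125 with 4 teams, 0.0625 with 5, 0.031 with 6 and 0.0078 with 8. If the Wilcoxon test was instead a rank-sum comparison of groups, 4 against 4 teams can reach 2/70 = 0.029.
- Friedman with 4 teams has 6⁴ = 1296 equally likely rank patterns. A statistic of 6.0 gives exp(−3) = 0.0498 by chi-square but 0.069 exactly, so the two fall on opposite sides of 0.05. The test can still reach 0.05: at its maximum, 8.0, the exact p is 6/1296 = 0.0046.

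**Precision.** By the t test, the pairwise difference detectable with 80% power is 0.71 SD with 32 units per group, and 1.02, 1.51 and 2.38 SD of the team score with 16, 8 and 4 teams.

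**The case against.** The strongest reply is that this is a gap in reporting. Nothing in the Statistical section says team scores were copied to members. A reader might infer that they were and that the teamwork p-values are therefore invalid. The documents do not support that: they are silent on the unit, and one row per team is equally compatible with them.

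A reader might also infer that the trial claims 32 independent units for teamwork and is underpowered for it. That does not follow either. The figure of 32 is given as people enrolled per group, never as the n of a team-rated outcome, and no effect size or power target is stated for the detectable differences to contradict.

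The scope is limited too. At most two of the seven instruments are involved. Medical task performance is not expressly linked to the video rating; the evaluators' scoring of resuscitation actions makes it probable. If members were scored separately, the copied-score figures do not apply. Extending the point to individually measured scales needs both an assumed intraclass correlation and team-based teaching. The Methods wording hints at such teaching but does not state it. With correlations of 0.05-0.20, Kruskal-Wallis would reject 6-8%, 7-15% and 11-29% for teams of 2, 4 and 8.

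All of this stands, and it lowers the severity. It does not dispose of the point. The argument that the GEE takes care of clustering holds only if the team is its subject, which is not stated. Even then, under my assumed specification, the uncorrected GEE exceeds 5%.

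**Conclusion.** The point holds in conditional form. The documents establish that teams were rated, that size is counted in individuals, and that no unit or cluster is named. They do not establish which unit was analysed.

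Only entry per member would put the rank tests seriously in error; with any team of more than one, the direction is certain and the size depends on team size. With entry per team, what remains is the unreported n, the coarseness of the rank tests when teams are few, and the uncorrected GEE. The last is the one component that exceeds its nominal level under either choice of unit, subject to the specification I assumed.

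I would rank this below a must-fix, because the serious error depends on a choice the documents leave open. It still calls for more than added wording, since a better analysis is available at little cost.

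**What to change.** State team size, number of teams per group, whether people or teams were allocated, and whether teams stayed the same over the three assessments. Friedman and signed-rank tests on teams need that stability.

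For the team-rated outcomes:

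- Use one record per team per time point, taking the mean of the two evaluators' scores, and report the number of teams as n.
- Use exact rank tests when teams are few.
- Make the team the GEE subject with a small-sample correction, for example Mancl-DeRouen with a t or F reference, or use a team-level permutation test. If the SPSS version named in the Statistical section does not offer this, run it elsewhere.

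If members were taught in teams, add a sensitivity analysis of the individually measured outcomes clustered on team.

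The plan is written in the past tense, so the cost appears to be SAP wording and re-analysis of existing data, with no new participants. The downside is fewer units: p-values may become less favourable, and with 5 or fewer teams per group the exact signed-rank test cannot reach 0.05, so within-group change would rest on the exact Friedman test and the corrected GEE. If one row per team was already used, only the reported n, the wording and possibly the GEE standard errors change.

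### No between-arm analysis is stated to adjust for the pretest; a covariate-adjusted comparison would usually be more precise and uses scores already collected

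*Combined protocol and SAP*

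**What the plan says.** The Methods section sets the measurement times: "Evaluations of effectiveness were conducted at three points: pretest, posttest, and at a three-month follow-up". It does not say whether every instrument was given at the pretest. There are three arms, "with each group comprising 32 individuals".

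The Statistical section names two between-arm analyses:

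- "To identify differences across the three groups, the study utilized the Kruskal-Wallis H-test". Neither the time point nor the score (posttest or change) is stated.
- "GEE analysis was employed to compare the effectiveness of the intervention across different time points among the three groups". No model terms, covariates or working correlation are given.

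The other tests are not between-arm comparisons adjusted for the pretest. "The Friedman test was used to evaluate changes within groups", and Wilcoxon tests serve for pairwise comparisons at the assessment points. The only baseline check described is a chi-squared test on demographics. The reason for using ranks is also given: "Given the data's deviation from a normal distribution, a non-parametric approach was adopted for analysis".

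The instruments are of two kinds. Some appear to be scored on the person ("knowledge of teamwork assessment, interprofessional collaboration scale, resuscitation knowledge scale"). Others are rated by blinded observers on the team ("to evaluate the medical team's resuscitation actions and teamwork behavior in scenario-based simulations through video observation").

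**The concern.** In a randomised trial with a baseline measure of the outcome, using that baseline as a covariate is usually the cheapest way to gain precision. Kruskal-Wallis cannot do this. Run on posttest scores, it ignores the pretest. Run on change scores, it subtracts the whole pretest, which adds noise when the correlation is low. A GEE with the pretest as one of three outcomes and free group-by-time terms also estimates a difference in change.

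Two things are at stake. With 32 per arm, a real difference between teaching methods is more easily missed. And if the arms happen to differ at pretest, posttest scores carry part of that difference forward, while change scores usually push the comparison the other way.

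**Working it through.** **Inputs from the documents.** Three arms of 32 (3 × 32 = 96, which agrees with the stated total); three assessment times; two-sided 5% level. No power, effect size, SD or pretest-posttest correlation r is given, so there is no sample-size calculation to reproduce. **Assumed:** r = 0.3 / 0.5 / 0.7, equal SDs at both times, independent people.

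**1. Variance of a pairwise arm difference**, relative to posttest only (2σ²/n): covariate adjustment gives 1 − r²; change scores give 2(1 − r). Their ratio, change over adjusted, is 2/(1 + r), which exceeds 1 whenever r < 1. The difference detectable with 80% power is (1.96 + 0.84) × √(2/32) × √factor = 0.70 × √factor, in SD units.

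| r | Adjusted: factor, detectable | Change: factor, detectable | Posttest: detectable |
|---|---|---|---|
| 0.3 | 0.91, 0.67 | 1.40, 0.83 | 0.70 |
| 0.5 | 0.75, 0.61 | 1.00, 0.70 | 0.70 |
| 0.7 | 0.51, 0.50 | 0.60, 0.54 | 0.70 |

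**2. Power of the three-arm tests** (20,000 simulated trials per setting, one arm +0.6 SD). Rank-ANCOVA here means Quade's method: rank both scores over all 96 people, regress posttest rank on pretest rank, and compare the residuals across arms.

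| Normal scores | r = 0.3 | 0.5 | 0.7 |
|---|---|---|---|
| Kruskal-Wallis, posttest | 65.7% | 66.4% | 66.6% |
| Kruskal-Wallis, change | 50.9% | 65.8% | 87.6% |
| Change-score ANOVA | 53.1% | 68.7% | 89.4% |
| Rank-ANCOVA | 69.8% | 77.9% | 91.0% |

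The two unadjusted options fail at opposite ends. Against posttest Kruskal-Wallis the gain is 4.1 / 11.5 / 24.4 points; against change-score ANOVA it is 16.7 / 9.2 / 1.6 points. Skewed and bounded scores behave similarly. With log-normal scores, posttest Kruskal-Wallis has about 66% and rank-ANCOVA 70 / 77 / 91%. On a 0–20 score with a ceiling, the figures are 62–63% and 67 / 74 / 87%. Without clustering, type I error of all tests was 4.5–5.2%.

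**3. High correlation.** In 10,000 simulated trials with a 0.4 SD effect, change-score ANOVA had 72.8% and rank-ANCOVA 72.0% at r = 0.8. At r = 0.9, Kruskal-Wallis on change had 95.1% and rank-ANCOVA 93.5%.

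**4. Chance imbalance.** With a pretest lead d and no effect, the posttest contrast is expected to shift by b × d and the change contrast by (b − 1) × d, where b = r × SDpost/SDpre. Change scores therefore over-correct when b < 1, which is r < 1 only if the SDs are equal. For d = 0.5 SD and equal SDs, the shifts are +0.15 / +0.25 / +0.35 SD for posttest and −0.35 / −0.25 / −0.15 SD for change. Simulated rejection rates were 7 / 11 / 15% for posttest Kruskal-Wallis, 13 / 11 / 9% for change-score ANOVA and about 5% for rank-ANCOVA. With r = 0.7 and SDpost/SDpre = 1.43, b = 0.7 × 1.43 = 1.00; change scores then showed no bias and 4.9% rejection. A lead of more than 0.5 SD over both other arms arises in about 1.2% of trials.

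**5. What the GEE estimates.** On one simulated data set, the group-by-time coefficient equalled the difference in mean change exactly (−0.521 in both). With group and time main effects only, the group coefficient was 0.222, because the pretest is averaged into it. The unstated terms decide which quantity is reported.

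**6. Dependence within teams.** With no effect, r = 0.5, assumed teams of 4 and within-team correlation 0.05 / 0.10 / 0.20 given the pretest, type I error on individual records is 6.5 / 8.6 / 12.3% for Kruskal-Wallis and 7.2 / 9.6 / 14.6% for rank-ANCOVA.

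**The case against.** The strongest reply is that the GEE already deals with the pretest. The sentence naming it speaks of effectiveness over the time points among the groups, which most naturally means group-by-time with the pretest as one time point. That stands as the likely reading, although the terms are not given. A reader might infer from the silence on covariates that the pretest is ignored; the documents do not support that. What remains is that a change comparison is less efficient than covariate adjustment, with a gap that is already small at r = 0.7.

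Second, the power figures assume independent people. The Methods section describes the evaluators as blind to the method taught to the team, which suggests teaching by team. If that is so, the figures fail even for individual scores, and on individual records rank-ANCOVA holds its level slightly worse than Kruskal-Wallis. This stands, and it shapes the remedy. The figures never applied to the team-rated outcomes, for which the number of teams is not given.

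Third, rank-ANCOVA is not uniformly best, and large imbalance is rare. Both are correct.

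Fourth, the Statistical section is in the past tense and refers to observed non-normality, so the analysis may be finished. That affects how a new analysis is labelled, not whether it is informative.

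**Conclusion.** The point holds as one of efficiency. No between-arm analysis is stated to adjust for the pretest, and for outcomes that have one, adjustment would usually sharpen the comparison. If r is near 0.5, power rises from about 66% to 78% for a 0.6 SD advantage in one arm. At r = 0.3 the gain over posttest Kruskal-Wallis is only about 4 points, and at r of about 0.8 and above the advantage over change-score tests is gone. These sizes rest on assumed r, effect and distribution, and on 32 independent people per arm.

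A reader might also conclude that the planned Kruskal-Wallis test is invalid. That does not follow: for independent observations, randomisation protects its overall type I error, and the raised rejection rates above are conditional on an uncommon imbalance. The unstated Kruskal-Wallis score and GEE terms are missing detail; the substantive matter is the absence of a stated pretest adjustment. It should be changed, with medium confidence.

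**What to change.** For each outcome that has a pretest, make a pretest-adjusted comparison the between-arm analysis at posttest and at three months:

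- **Test:** rank-ANCOVA on the pretest in place of Kruskal-Wallis. This keeps the rank-based approach chosen for non-normal data.
- **Estimate:** pretest-adjusted mean differences with 95% CI. Use ANCOVA at each time with HC3 standard errors (simulated coverage 94.6–96.0%, against 92.6–95.9% for classical standard errors). Alternatively, use a GEE on the two later times with arm, time, arm × time and pretest, and a small-sample correction. In simulation the plain sandwich gave 6.2–6.8% type I error; Mancl-DeRouen with an F reference gave 4.1–4.9%.
- **Team-rated outcomes:** one record per team, with the team's pretest as covariate. With an assumed 4–16 teams per arm, simulated type I error was 4.8–5.1% for ANCOVA and 4.7–5.8% for rank-ANCOVA.
- **Individual scores, if people were taught in fixed teams:** the same method on team means. Rank-ANCOVA on individual records does not cure dependence within teams.
- **Wording:** state the score and time point for any Kruskal-Wallis test that is kept, and the GEE's terms, contrast, working correlation and clustering unit.

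If the data are already analysed, run this on the existing data and label it as added later.

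The cost is SAP wording, one degree of freedom, a modest amount of extra analysis (including the variance correction and team-level records where needed), and a slight loss against change scores if r proves very high. No new data are needed.
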